4.2.1 Nivolumab

Treatment will be administered on an outpatient basis. Reported adverse events and potential risks are described below. No investigational or commercial agents or therapies other than those described below may be administered with the intent to treat the patient's malignancy.

Nivolumab will be administered at a dose of 240mg (combined with ipilimumab) as an intravenous infusion over approximately 30 minutes (-5 / +15 minutes)

NU Study Number: NU 16B07
Other Study Number: CA 209-782

every 2 weeks for the first 16 weeks (1 cycle = 12 weeks). Starting with Cycle 2 Day 29, nivolumab will be given at 480mg IV over approximately 60 minutes (-10 / +15 minutes) every 4 weeks until disease progression, unacceptable toxicity, or withdrawal of consent.

NOTE: The first two nivolumab doses of Cycle 2 will be given at 240mg q2weeks.

There will be no dose escalations or reductions of nivolumab allowed. Subjects may be dosed no less than 12 days or 24 days from the previous dose (for 240mg and 480mg doses, respectively). There are no pre-medications recommended for nivolumab on the first cycle. If an acute infusion reaction is noted, subjects should be managed according to Section 4.3.3.

Nivolumab is to be administered as a 30-minute (-5 / +15 minutes) or 60-minute (-10 / +15 minutes) IV infusion (for 240mg and 480mg, respectively), using a volumetric pump with a 0.2- 1.2 micron low-protein binding in-line filter at the protocol-specified dose. The drug can be diluted with 0.9% Sodium Chloride or 5% Dextrose for delivery but the total drug concentration of the solution cannot be below 0.35 mg/mL. It is not to be administered as an IV push or bolus injection. At the end of the infusion, flush the line with a sufficient quantity of normal saline.

Subjects will be monitored continuously for AEs while on study. Treatment delay or discontinuation will be based on specific laboratory and adverse event criteria.

Early recognition and management may mitigate severe toxicity. Evaluation and Management Guidelines were developed to assist investigators and can be found in the Investigator Brochure:

- Suspected Pulmonary Toxicity
- Diarrhea and Colitis
- Suspected Hepatotoxicity (including asymptomatic liver function tests [LFT] elevations)
- Suspected Endocrinopathy
- Nephrotoxicity

4.2.2 Ipilimumab

Ipilimumab will be administered at a dose of 1mg/Kg as an intravenous infusion over approximately 90 minutes (-5 / +15 minutes) every 6 weeks until disease progression, unacceptable toxicity, or withdrawal of consent. Dosing will be based on actual body weight in kg on the day of the infusion. On days when both ipilimumab and nivolumab are administered, nivolumab should be given first, followed by ipilimumab ~30 minutes later.

There will be no dose escalations or reductions of ipilimumab allowed. There are no pre-medications recommended for ipilimumab on the first cycle. If an acute infusion reaction is noted subjects should be managed according to Section 4.3.3.

Ipilimumab is to be administered as a 90-minute IV infusion (a window of -5 / +15 minutes is allowed), using a volumetric pump with a 0.2/1.2 micron in-line filter at the protocol-specified dose. The drug can be diluted with 0.9% normal saline for delivery but the total drug concentration of the solution cannot be below 1 mg/mL. It is not to be administered as an IV push or bolus injection. At the end of the infusion, flush the line with a sufficient quantity of normal saline.

Subjects will be monitored continuously for AEs while on study. Treatment delays or discontinuation will be based on specific laboratory and adverse event criteria.

NU Study Number: NU 16B07
Other Study Number: CA 209-782

Early recognition and management may mitigate severe toxicity. Evaluation and Management Guidelines were developed to assist investigators and can be found in the Investigator Brochure:

- Suspected Pulmonary Toxicity
- Diarrhea and Colitis
- Suspected Hepatotoxicity (including asymptomatic liver function tests [LFT] elevations)
- Suspected Endocrinopathy
- Nephrotoxicity

4.3 Toxicity Management & Dose Delays

Any patient who receives at least one dose of study therapy will be evaluable for toxicity endpoints. Each patient will be assessed for the development of toxicity according to the timeframe referenced in the Schedule of Events table). Toxicity will be assessed according to the NCI CTCAE v. 4.03.

4.3.1 Dose delays: Ipilimumab and/or nivolumab

There will be no dose modifications allowed for management of toxicities.

Should the treating physician decide to delay treatment given suspicion for a drug-related side effect, the side effect should be attributed to one study drug to the best of the physician's ability. Either ipilimumab or nivolumab should be delayed based on this attribution, or both if a definite attribution is not possible. Both drugs can be held for a maximum of 56 days.

Ipilimumab and/or nivolumab administration should be delayed for the following until resolution to \leq Grade 1:

- Any Grade \geq 2 non-skin, drug-related adverse event, with the following exceptions:
 - Grade 2 drug-related fatigue or laboratory abnormalities do not require a treatment delay
 - Any Grade 3 skin, drug-related adverse event
 - Any Grade 3 drug-related laboratory abnormality, with the following exceptions for lymphopenia, leukopenia, AST, ALT, or total bilirubin:
 - Grade 3 lymphopenia or leukopenia does not require dose delay
 - If a subject has a baseline AST, ALT or total bilirubin that is within normal limits, delay dosing for drug-related Grade \geq 2 toxicity
 - If a subject has baseline AST, ALT, or total bilirubin within the Grade 1 toxicity range, delay dosing for drug-related Grade \geq 3 toxicity
- Any adverse event, laboratory abnormality, or intercurrent illness which, in the judgment of the investigator, warrants delaying the dose of study medication.

Immunotherapy agents such as nivolumab and ipilimumab are associated with AEs that can differ in severity and duration compared to other therapeutic classes of medications. Early recognition and management of AEs associated with nivolumab can mitigate severe toxicity. Corticosteroids are the primary therapy for drug-related AEs. Management algorithms have been developed to assist investigators in assessing and managing nivolumab associated AEs, which can be found in Appendix D of this protocol. The guidance provided in these algorithms should not replace the Investigator's medical judgment.

NU Study Number: NU 16B07
Other Study Number: CA 209-782

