4.3.2 Treatment discontinuation: Ipilimumab and/or nivolumab

Should the treating physician decide to discontinue treatment given suspicion for a drug related side effect, the side effect (adverse event) should be attributed to one study drug to the best of the physician's ability. Either ipilimumab or nivolumab should be discontinued based on this attribution, or both if definite attribution is not possible.

Ipilimumab and/or nivolumab should be discontinued permanently for the following:

- Any Grade 2 drug-related uveitis, eye pain, or blurred vision that does not respond to topical therapy and does not improve to Grade 1 severity within the re-treatment period OR requires systemic treatment
- Any Grade 3 non-skin, drug-related adverse event lasting > 7 days, with the following exceptions for laboratory abnormalities, drug-related uveitis, pneumonitis, bronchospasm, hypersensitivity reactions, infusion reactions, and endocrinopathies:
 - Grade 3 drug-related uveitis, pneumonitis, bronchospasm, hypersensitivity reaction, or infusion reaction of any duration requires discontinuation
 - Grade 3 drug endocrinopathies adequately controlled with only physiologic hormone replacement do not require discontinuation
 - Grade 3 drug-related laboratory abnormalities do not require treatment discontinuation except:
 - Grade 3 drug-related thrombocytopenia > 7 days or associated with bleeding (aside from minor bleeds \leq Grade 1) requires discontinuation
 - Any drug-related liver function test (LFT) abnormality that meets the following criteria require discontinuation:
 - AST or ALT $>$ 5-10 x ULN for > 2 weeks
 - AST or ALT $>$ 10 xUL
 - Total bilirubin $>$ 5 x ULN
 - Concurrent AST or ALT $>$ 3 xULN and total bilirubin $>$ 2 x ULN
- Any Grade 4 drug-related adverse event or laboratory abnormality, except for the following events which do not require discontinuation:
 - Grade 4 neutropenia $<$ 7 days
 - Grade 4 lymphopenia or leukopenia
 - Isolated Grade 4 amylase or lipase abnormalities that are not associated with symptoms or clinical manifestations of pancreatitis. PI and Data Monitoring Committee (DMC) should be consulted for Grade 4 amylase or lipase abnormalities.
 - Isolated Grade 4 electrolyte imbalances/abnormalities that are not associated with clinical sequelae and are corrected with supplementation/appropriate management within 72 hours of their onset

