- Grade 4 drug-related endocrinopathy adverse events, such as adrenal insufficiency, ACTH deficiency, hyper- or hypothyroidism, or glucose intolerance, which resolve or are adequately controlled with physiologic hormone replacement (corticosteroids, thyroid hormones) or glucose-controlling agents, respectively, may not require discontinuation.

NU Study Number: NU 16B07
Other Study Number: CA 209-782

Any event that leads to interruption in dosing lasting > 56 days (8 weeks) from the previous dose requires discontinuation.

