7.2 Definitions & Descriptions

7.2.1 Adverse Event

An adverse event (AE) is any untoward medical occurrence in a patient receiving study treatment and which does not necessarily have a causal relationship with this treatment. An AE can therefore be any unfavorable and unintended sign (including an abnormal laboratory finding), symptom, or disease temporally associated with the use of an experimental intervention, whether or not related to the intervention.

Recording of AEs should be done in a concise manner using standard, acceptable medical terms. In general, AEs are not procedures or measurements, but should reflect the reason for the procedure or the diagnosis based on the abnormal measurement. Preexisting conditions that worsen in severity or frequency during the study should also be recorded (a preexisting condition that does not worsen is not an AE). Further, a procedure or surgery is not an AE; rather, the event leading to the procedure or surgery is considered an AE.

If a specific medical diagnosis has been made, that diagnosis or syndrome should be recorded as the AE whenever possible. However, a complete description of the signs, symptoms and investigations which led to the diagnosis should be provided. For example, if clinically significant elevations of liver function tests are known to be secondary to hepatitis, "hepatitis" and not "elevated liver function tests" should be recorded. If the cause is not known, the abnormal test or finding should be recorded as an AE, using appropriate medical terminology (e.g/ thrombocytopenia, peripheral edema, QT prolongation).

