8.2.10 Side effects

Immune-related adverse events have been associated with ipilimumab when administered intravenously.

Below are safety data from 131 patients with metastatic melanoma who received ipilimumab as monotherapy in a phase 3 trial.

Very Frequent – Expected to occur in more than 20% of people (more than 20 out of 100 people): Fatigue (42%), Pruritus (24.4%), Decreased appetite (26.7%), Diarrhea (32.8%), Nausea (35.1%), Constipation (20.6%), Vomiting (23.7%),

Frequent - Expected to occur in 10% to 20% of people (10 to 20 out of 100 people): Abdominal pain (15.3%), pyrexia (12.2%), headache (14.5%), Cough (16%), dyspnea (14.5%), anemia (11.5%), rash (19.1)

NU Study Number: NU 16B07
Other Study Number: CA 209-782

Not Frequent – Expected to occur in less than 10% of people (less than 10 out of 100 people): vitiligo, colitis, hypothyroidism, hypopituitarism and adrenal insufficiency, increased aspartate aminotransferase and alanine aminotransferase

Deaths thought to be related to ipilimumab when given alone were reported in approximately 3 % of subjects treated (approximately 4 out 131 people).

For the most recent safety update, please refer to the current Investigator's Brochure or Study Agent Prescribing Information.

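### Section 4.3.1 has no resume rule for an endocrinopathy controlled on replacement but still above Grade 1, so the 56-day stop can override 4.3.2's own exceptions

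*Combined protocol and SAP*

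**What the plan says.** Section 4.3.1 delays the drug to which an event is attributed, or both drugs if attribution is not possible. The governing line is "Ipilimumab and/or nivolumab administration should be delayed for the following until resolution to" Grade 1 or lower. It covers any non-skin drug-related event of Grade 2 or higher. The listed exceptions concern Grade 2 fatigue, Grade 2 laboratory abnormalities, Grade 3 lymphopenia or leukopenia, and liver tests judged against baseline. Endocrinopathy is not named. The last bullet lets the investigator add a delay for other reasons; it does not let the investigator end one.

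Section 4.3.2 treats endocrine events separately when it lists reasons for permanent discontinuation:

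- Grade 3: "Grade 3 drug endocrinopathies adequately controlled with only physiologic hormone replacement do not require discontinuation".
- Grade 4: endocrinopathies "which resolve or are adequately controlled with physiologic hormone replacement (corticosteroids, thyroid hormones) or glucose-controlling agents, respectively, may not require discontinuation".

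The section closes with a rule that has no exception: "Any event that leads to interruption in dosing lasting > 56 days (8 weeks) from the previous dose requires discontinuation".

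Two sources of guidance are cited. Section 4.3.1 points to Appendix D: "Management algorithms have been developed to assist investigators in assessing and managing nivolumab associated AEs". Section 4.2.2 says: "Evaluation and Management Guidelines were developed to assist investigators and can be found in the Investigator Brochure". Neither the Appendix D endocrinopathy figure nor the brochure text can be read in the available documents.

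**The concern.** 4.3.1 asks whether the event has come down to Grade 1. The endocrine exceptions in 4.3.2 ask whether it is controlled. An event can pass the second test and fail the first. It then stays on hold until the 56-day line removes the drug, although the same section says that this kind of event need not end treatment.

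What is at stake is drug exposure and consistent handling. A patient with a controlled endocrine event could permanently lose one or both study drugs. A physician who redoses because the event is controlled would depart from 4.3.1, while 11.6 asks for conduct exactly as the protocol describes. Two similar patients could therefore be managed differently. The situation is foreseeable: 8.2.10 lists "hypothyroidism, hypopituitarism and adrenal insufficiency" among the side effects of ipilimumab.

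**Working it through.** **Step 1. The stated limit.** 4.3.2 gives 56 days and 8 weeks. 8 × 7 = 56, so the figure reproduces.

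**Step 2. Do the exceptions cover events that persist?** Yes. The Grade 3 exception qualifies a rule for events lasting more than 7 days. The Grade 4 exception lists resolution and adequate control as alternatives. Both therefore reach events that are controlled without having resolved.

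**Step 3. Follow a controlled endocrinopathy through both sections.**

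| Current grade | 4.3.1 hold | Grade-based stop in 4.3.2 | More than 56 days from previous dose |
|---|---|---|---|
| 1 or lower | Released | None | Not reached if the grade falls in time |
| 2 | Continues | None for endocrine events | Stop required |
| 3 | Continues | Averted by the exception | Stop required |
| 4 | Continues | May be averted by the exception | Stop required |

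The rules collide in the last three rows. For Grades 3 and 4 the result runs against the stated exceptions. For Grade 2 the drug is lost for an event milder than those the exceptions protect.

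**Step 4. Does the laboratory exemption help at Grade 2?** Only if the event is recorded as a laboratory abnormality. Section 7.2.1 points the other way: "If a specific medical diagnosis has been made, that diagnosis or syndrome should be recorded as the AE whenever possible". A diagnosed hypothyroidism would normally be entered as the diagnosis, which is not exempt.

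**Step 5. Time available.** 4.3.2 counts from the previous dose, so time past the due date = 56 − dosing interval. The intervals are in 4.1.

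- Ipilimumab every 6 weeks: 56 − 42 = 14 days.
- Nivolumab 480 mg every 4 weeks: 56 − 28 = 28 days.
- Nivolumab 240 mg every 2 weeks: 56 − 14 = 42 days.

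The Amendment 1 rationale in Appendix E counts the same way and also reaches 28 days for four-weekly nivolumab. Section 4.3.1 separately caps a hold at 56 days without naming a starting point; the 4.3.2 count binds first.

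These margins apply to every toxicity, not only endocrine events, and they run from the missed dose. An event that begins d days after the last dose has 56 − d days in which to reach Grade 1, so an early onset leaves nearly the full 56 days.

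**Step 6. Does the rest of the protocol accept dosing with a controlled endocrine deficiency?** It does. The note to 3.2.6 admits patients with type I diabetes, or with residual autoimmune hypothyroidism needing replacement only. Section 4.5.1 permits low-dose adrenal replacement when there is no active autoimmune disease. Lymphopenia and leukopenia are relieved in both places: Grade 3 from the hold and Grade 4 from discontinuation. Endocrinopathy is relieved only from discontinuation, which looks like an omission.

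**The case against.** The strongest reply concerns grading. The conflict arises only if a controlled endocrinopathy is still graded 2 or higher. Grading follows CTCAE v4.03, whose text is not in the documents. That control differs from resolution does not show that a controlled event sits above Grade 1, and 4.3.1 asks only for Grade 1, not for full resolution. This stands as a condition on the point: where a controlled event is regraded to 1 within the limit, nothing goes wrong.

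Second, the Appendix D endocrinopathy algorithm may contain a resume instruction, and 4.3.1 says that the algorithms do not replace medical judgment. That possibility also stands. But the algorithms are offered to assist investigators, and they would not amend the wording of 4.3.1 or the 56-day requirement.

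Third, the two sections can be read as a cautious layered rule, because not having to stop is not the same as permission to redose. That is fair as to 4.3.2, which grants no such permission. It does not explain why a controlled event is spared one permanent stop and then given another.

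Fourth, the hold is worded as a recommendation and attribution may confine it to one drug. Both are true and limit the reach. The 56-day line, however, is worded as a requirement.

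A reader might infer that the 4.3.2 exceptions are void. They are not: they still avert the stop for Grade 3 events beyond 7 days and may avert the immediate stop at Grade 4. A reader might also infer that one missed ipilimumab dose ends ipilimumab because the next six-weekly date falls beyond day 56. The documents do not say that a delayed dose must wait for its original calendar date.

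**Conclusion.** The point holds in conditional form. For a drug-related endocrinopathy that is controlled on replacement but remains at Grade 2 or higher, 4.3.1 keeps the attributed drug, or both, on hold, and 4.3.2 ends it once 56 days have passed since the previous dose. The endocrine exceptions are then limited to a reprieve within that window, with 14, 28 or 42 days past the due date depending on drug and schedule.

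The conclusion assumes that some controlled events stay above Grade 1, that they are recorded as diagnoses, and that the readable text of 4.3.1 governs. The number of patients affected cannot be derived from the documents.

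A reader might infer a threat to the primary analysis. The documents do not support that for ascertainment: 4.7 continues imaging until progression after a toxicity stop. No sample size, power or type I error figure depends on these rules. The consequence is avoidable loss of study drug and inconsistent handling, which is enough to justify a correction in the next amendment.

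**What to change.** Add one sentence to 4.3.1, for example:

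> The held drug may be resumed once a drug-related endocrinopathy is adequately controlled on physiologic hormone replacement alone, even if it is still above Grade 1, provided that no discontinuation criterion in 4.3.2 is met and the investigator judges redosing appropriate. For glucose intolerance, control on glucose-lowering treatment also qualifies where 4.3.2 does not require discontinuation.

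The last clause is needed because the Grade 3 exception names hormone replacement only, while the Grade 4 exception also names glucose-controlling agents.

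Keep the 56-day line for events not controlled in time, and keep the investigator's freedom to delay a dose. Check the sentence against the Appendix D endocrinopathy algorithm so that the two agree.

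The cost is one sentence in the next amendment, with no extra visits, tests or patients. The downside is that some patients would be redosed with a controlled event above Grade 1, which the 4.3.2 exceptions already contemplate.

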4.3.2 Treatment discontinuation: Ipilimumab and/or nivolumab

Should the treating physician decide to discontinue treatment given suspicion for a drug related side effect, the side effect (adverse event) should be attributed to one study drug to the best of the physician's ability. Either ipilimumab or nivolumab should be discontinued based on this attribution, or both if definite attribution is not possible.

Ipilimumab and/or nivolumab should be discontinued permanently for the following:

- Any Grade 2 drug-related uveitis, eye pain, or blurred vision that does not respond to topical therapy and does not improve to Grade 1 severity within the re-treatment period OR requires systemic treatment
- Any Grade 3 non-skin, drug-related adverse event lasting > 7 days, with the following exceptions for laboratory abnormalities, drug-related uveitis, pneumonitis, bronchospasm, hypersensitivity reactions, infusion reactions, and endocrinopathies:
 - Grade 3 drug-related uveitis, pneumonitis, bronchospasm, hypersensitivity reaction, or infusion reaction of any duration requires discontinuation
 - Grade 3 drug endocrinopathies adequately controlled with only physiologic hormone replacement do not require discontinuation
 - Grade 3 drug-related laboratory abnormalities do not require treatment discontinuation except:
 - Grade 3 drug-related thrombocytopenia > 7 days or associated with bleeding (aside from minor bleeds \leq Grade 1) requires discontinuation
 - Any drug-related liver function test (LFT) abnormality that meets the following criteria require discontinuation:
 - AST or ALT $>$ 5-10 x ULN for > 2 weeks
 - AST or ALT $>$ 10 xUL
 - Total bilirubin $>$ 5 x ULN
 - Concurrent AST or ALT $>$ 3 xULN and total bilirubin $>$ 2 x ULN
- Any Grade 4 drug-related adverse event or laboratory abnormality, except for the following events which do not require discontinuation:
 - Grade 4 neutropenia $<$ 7 days
 - Grade 4 lymphopenia or leukopenia
 - Isolated Grade 4 amylase or lipase abnormalities that are not associated with symptoms or clinical manifestations of pancreatitis. PI and Data Monitoring Committee (DMC) should be consulted for Grade 4 amylase or lipase abnormalities.
 - Isolated Grade 4 electrolyte imbalances/abnormalities that are not associated with clinical sequelae and are corrected with supplementation/appropriate management within 72 hours of their onset
- Grade 4 drug-related endocrinopathy adverse events, such as adrenal insufficiency, ACTH deficiency, hyper- or hypothyroidism, or glucose intolerance, which resolve or are adequately controlled with physiologic hormone replacement (corticosteroids, thyroid hormones) or glucose-controlling agents, respectively, may not require discontinuation.

NU Study Number: NU 16B07
Other Study Number: CA 209-782

Any event that leads to interruption in dosing lasting > 56 days (8 weeks) from the previous dose requires discontinuation.

